10.6 BPRS+

BPRS+ total score data will be summarised by visit (*Table 14.3.6.5*) and BPRS+ symptom score data will be summarised categorically by visit (*Table 14.3.6.6*). BPRS+ data will also be listed (*Listing 16.2.9.3*).

11 EFFICACY

The FAS will be used for all efficacy-related evaluations.

The summaries and analyses will be presented overall.

Since there is only one treatment group, there will be no formal statistical testing of any hypothesis. In some cases, 95% confidence intervals (CIs) will be reported but these are to be interpreted as exploratory.

11.1 Secondary Efficacy Endpoint(s)

The secondary endpoints are:

- Change in CAPS-5 total symptom severity score and criteria scores from baseline
- Change in PCL-5 total symptom severity score and cluster severity scores from baseline
- Change in SDS total score from baseline
- Change in EQ-5D-5L index score from baseline
- Proportion of participants with response (defined as a ≥ 15 point improvement on the CAPS-5 total score from baseline)
- Proportion of participants with remission (defined as CAPS-5 total score ≤ 20)

11.1.1 Main Analysis

Total/total severity/index score values and their changes from baseline at each post-baseline timepoint will be descriptively summarised using statistics for continuous variables including 95% CIs for the FAS. Both actual values and their change from baseline will also be graphically displayed as line plots for the FAS. All observed scale data will also be listed. These summaries, figures and listings will be presented for the scales below:

- CAPS-5 (*Table 14.2.2.1*, *Figure 14.2.2.1*, *Listing 16.2.6.1*)
- PCL-5 (*Table 14.2.2.2*, *Figure 14.2.2.2*, *Listing 16.2.6.2*)
- SDS (*Table 14.2.2.3*, *Figure 14.2.2.3*, *Listing 16.2.6.3*)
- EQ-5D-5L (*Table 14.2.2.4*, *Figure 14.2.2.4*, *Listing 16.2.6.4*)

The proportion of CAPS-5 responders (defined as a ≥ 15 point improvement on the CAPS-5 total score from Baseline) and CAPS-5 remitters (defined as CAPS-5 total score ≤ 20), will be descriptively summarised alongside 95% asymptotic CIs at each post-baseline timepoint (*Table 14.2.2.5* for response and *Table 14.2.2.6* for remission) and graphically

displayed via bar charts including the estimated 95% Wald-type CIs (*Figure 14.2.2.5* for response and *Figure 14.2.2.6* for remission). At each timepoint separate proportions will be calculated using both the total number of participants in the FAS (N) and the total number of participants with available data at a particular visit as the denominator (n*).

CIs will be Wald-type asymptotic intervals based on the Normal approximation to the binomial distribution, obtained in SAS as follows:

```
ods output BinomialCLs = <output-dataset>;
proc freq data = ;
  by avisitn;
  tables aval / binomial (level = 2 cl = wald);
run;
```

Participant's status as a responder/remitter at each timepoint will be listed (*Listing 16.2.6.1*).

Participant's status as a remitter at each timepoint will be listed (*Listing 16.2.6.1*).

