13.5 Data Handling

Procedures for the handling of any missing, unused or spurious data will be described in the SAP.

13.5.1 *Analysis of Efficacy*

Since this is a single treatment open-label study, no statistical testing will be performed.

The FAS and the PP Analysis Set will both be used for all efficacy-related endpoints, if the two sets are not identical. For each of the secondary (CAPS-5, PCL-5, SDS and EQ-5D-5L (including EQ VAS)) and some exploratory endpoints (PACT, RAS) measuring changes from baseline, summary statistics will be provided. In addition, 95% confidence intervals for changes from baseline as well as for proportions of responders and remitters based on the CAPS-5 will be provided. Graphical displays will also be created for a subset of the efficacy endpoints to visualise their profile over time.

Analysis of all exploratory endpoints will be further detailed in the SAP.

13.5.2 *Analysis of Safety*

13.5.2.1 *Adverse Events*

AEs will be coded by System Organ Class (SOC) and Preferred Term (PT) using the Medical Dictionary for Regulatory Activities (MedDRA) classification.

A TEAE is defined as any AE that has an onset on or after taking study drug, or any pre-existing condition that has worsened on or after taking study drug.

The frequency and incidence of TEAEs will be summarised by SOC and PT. Summaries will also include, but not limited to, relationship to study drug and maximum severity. The summary will be sorted by International Agreed Order for SOC and alphabetical order for Preferred Term.

For each of the summaries produced at the participant level, multiple occurrences of the same event within a participant will be counted once in the summaries by SOC and Preferred Term; multiple occurrences of the same event within a participant will be counted once in the maximum severity category (severe > moderate > mild) and/or maximum drug relationship category (reasonable possibility/no reasonable possibility). If severity or relationship is found to be missing, the most severe occurrence will be imputed for that particular summary.

AESIs will also be presented using the same logic as for general AE summary tables, including patient incidence and event counts.

These summaries will also present the number of events that occurred, so multiple occurrences of the same event within a participant will all be accounted for in the maximum intensity category and maximum relationship category they were classed as.

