4.6 Sample Size Considerations

The sample size is not based on a formal statistical evaluation but is considered to be adequate to meet the objectives of the study. Approximately 20 participants are expected to be enrolled in the study.

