1. BACKGROUND

This document details changes and / or additions to the planned statistical analyses for Compass Pathfinder Limited protocol COMP 201 study previously described in version 1.0 of the Statistical Analysis Plan (SAP) dated 05-March-2024.

These amendments were made post database lock but since the study was open label there was no unblinding step.

Rationale for Addendum:

1. To include instructions on how to derive the CAPS-5 cluster severity scores to be able to summarise, graphically display, and list these scores.
2. To include a summary of concomitant medications relative to COMP360 dose (i.e. medications that were taken pre-dose, post-dose, and overall).
3. To include individual participant plots of the CAPS-5 total scores.
4. To include details of scatter plots with Spearman's rank correlation coefficients to be produced for each dimension of the 5D-ASC on the x-axis and change from baseline in CAPS-5 total score on the y-axis.
5. To clarify in Section 11.2 that only individual item scores for the Resilience Adult Scale (RAS) are to be listed.
6. To remove Table 14.1.3.10 'Life Event Checklist for DSM-5 (LEC-5) – Safety Analysis Set' in Section 16 as this summary is redundant as this information is incorporated into Table 14.1.3.8 'Other Baseline Characteristics – Safety Analysis Set'.
7. To include a summary table and listing to report results for the Modified Discontinuation Emergent Signs and Symptoms Scale (mDESS).

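### Wald 95% intervals for CAPS-5 response and remission at about 20 participants under-cover, badly near 0% or 100%, and have zero width at 0/n or n/n

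*SAP*

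**What the plan says.** Protocol 13.5.1 promises intervals for these endpoints without naming a method: "95% confidence intervals for changes from baseline as well as for proportions of responders and remitters based on the CAPS-5 will be provided".

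SAP 11.1.1 supplies the method. It asks for asymptotic 95% intervals in Tables 14.2.2.5 (response) and 14.2.2.6 (remission). The matching figures are "displayed via bar charts including the estimated 95% Wald-type CIs". It then states that "CIs will be Wald-type asymptotic intervals based on the Normal approximation to the binomial distribution", and the sample code agrees: "tables aval / binomial (level = 2 cl = wald". No exact or score interval is offered, and there is no rule for counts of 0 or n.

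On sample size, SAP 4.6 says "Approximately 20 participants are expected to be enrolled in the study"; Protocol 6.1 says up to 20. On denominators, SAP 11.1.1 says "At each timepoint separate proportions will be calculated using both the total number of participants in the FAS (N") and, separately, the number with data at the visit (n*). It does not say in terms which of the two proportions the interval belongs to.

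SAP 11 sets the status of all such intervals: "In some cases, 95% confidence intervals (CIs) will be reported but these are to be interpreted as exploratory". The post-lock addendum changes several outputs but not this method.

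**The concern.** The Wald interval rests on a normal approximation that is poor at n of about 20 and fails near the ends of the scale, because its width is estimated from the observed proportion alone. As that proportion approaches 0 or 1, the estimated standard error shrinks to nothing.

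With no hypothesis test, the estimate and its interval are the whole reported result for response and remission. If the observed rate is very high or very low, the displayed bar overstates certainty, and at 0% or 100% it shows no uncertainty at all. The error has a direction: at high observed rates the Wald lower limit is too favourable.

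**Working it through.** **Inputs.** n = 20 (SAP 4.6; Protocol 6.1), with n = 18 and 15 as assumed values of n*. Two-sided 95% level, z = 1.96. The documents give no expected response or remission rate, so the true rate p is taken over a range. They also state no coverage or precision figure, so there is nothing to reproduce except the nominal 95%.

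**Formulas.** With x responders and p̂ = x/n:
- Wald: p̂ ± z√(p̂(1 − p̂)/n).
- Wilson: [p̂ + z²/2n ± z√(p̂(1 − p̂)/n + z²/4n²)] / (1 + z²/n).
- Clopper-Pearson: the exact binomial limits.
- Exact coverage at p: the sum of Binomial(n, p) probabilities over every x whose interval contains p.
- Probability of a zero-width Wald interval: pⁿ + (1 − p)ⁿ.

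**Two worked values, Wald, n = 20.**
- p = 0.95: the interval contains 0.95 only for x = 16 to 19. At x = 15 it is 0.75 ± 0.190 = [0.560, 0.940]; at x = 20 it is [1, 1]. Coverage = 1 − P(X = 20) − P(X ≤ 15) = 1 − 0.3585 − 0.0026 = 0.639.
- p = 0.50: the interval contains 0.50 for x = 6 to 14. Coverage = 1 − 2 × P(X ≤ 5) = 1 − 2 × 0.0207 = 0.959.

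**Coverage at n = 20** (symmetric about 0.50):

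| True rate | Wald | Wilson | Clopper-Pearson | P(zero-width Wald) |
|---|---|---|---|---|
| 0.50 | 95.9% | 95.9% | 95.9% | <0.1% |
| 0.40 / 0.60 | 92.8% | 96.3% | 96.3% | <0.1% |
| 0.30 / 0.70 | 94.7% | 97.5% | 97.5% | <0.1% |
| 0.25 / 0.75 | 89.5% | 93.5% | 96.2% | 0.3% |
| 0.20 / 0.80 | 92.1% | 95.6% | 97.8% | 1.2% |
| 0.15 / 0.85 | 81.9% | 97.8% | 97.8% | 3.9% |
| 0.10 / 0.90 | 87.6% | 95.7% | 98.9% | 12.2% |
| 0.05 / 0.95 | 63.9% | 92.5% | 98.4% | 35.8% |

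**Means on a 0.001 grid, n = 20.**
- True rates 0.30–0.70: Wald 92.4%, Wilson 95.1%, Clopper-Pearson 97.1%.
- True rates 0.05–0.95: Wald 89.8%, Wilson 95.4%, Clopper-Pearson 97.6%.
- Over 0.05–0.95, Wald is below 95% at 99.4% of rates (minimum 63.9%) and Wilson at about 40% (minimum 91.7%). Clopper-Pearson never is.

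**Smaller n\*.** Mean Wald coverage over 0.05–0.95 is 89.1% at n = 18 and 87.6% at n = 15.

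**Limits at n = 20:**

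| Count | Wald | Wilson | Clopper-Pearson | Widths in points |
|---|---|---|---|---|
| 10/20 | 28.1–71.9% | 29.9–70.1% | 27.2–72.8% | 43.8, 40.1, 45.6 |
| 16/20 | 62.5–97.5% | 58.4–91.9% | 56.3–94.3% | 35.1, 33.5, 37.9 |
| 19/20 | 85.5–104.5% | 76.4–99.1% | 75.1–99.9% | 19.1, 22.7, 24.7 |
| 20/20 | 100–100% | 83.9–100% | 83.2–100% | 0, 16.1, 16.8 |

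Untruncated Wald limits leave 0–100% at 1–3 and 17–19 of 20. In the middle of the range the fault is centring more than width: at 16/20 Wilson is slightly narrower than Wald but shifted toward 50%.

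**Denominator (assumed case).** Take 16 responders, all 16 participants with data, and N = 20. On n* = 16 Wald gives [100%, 100%]; on N = 20 it gives [62.5%, 97.5%]. The two can differ because SAP 6 and 12 now keep participants without a post-baseline assessment in the FAS.

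**The case against.** The strongest reply is that nothing is decided on these intervals. The study is descriptive, its primary objective is safety, and the SAP calls the intervals exploratory. The CAPS-5 change score has its own interval, and responder status is listed by participant, so a reader can recompute any interval from x and n. All of this is true, and it caps the importance of the point. It does not make a bar labelled 95% correct when its coverage is materially lower.

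Second, the severe figures need a true rate near 5% or 95%, and nothing in the documents suggests such a rate. Between 30% and 70% the average shortfall is about 2.6 points (95 − 92.4), and at 10/20 no one would read Wald and Wilson differently. That stands. Equally, nothing rules out extreme results, and the SAP has no fallback if they occur.

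Third, Wilson also dips below 95%. It does, but its lowest coverage over 0.05–0.95 is 91.7% against 63.9% for Wald.

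Fourth, the denominator gap can be read away: each proportion may be meant to carry its own interval, and SAP 7 makes N the default denominator. That reading is reasonable. What remains is a request for clarification, mainly about which proportion the bar charts show; the main point does not depend on it.

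Fifth, replacing a prespecified method after lock in an open-label study could look driven by the data. This is a fair caution about how the change is made.

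**Conclusion.** The concern holds and should be fixed, though no decision turns on it. As written, the intervals under-cover at almost every true rate at n = 20, modestly in the middle and severely near the ends, and they collapse to a point at 0/n and n/n. The coverage figures are exact for a binomial count with n = 20. How much it matters in this trial depends on the observed rates, for which the documents give no expectation, and on how many participants have CAPS-5 data at Weeks 4 and 12. Out-of-range limits would appear only if the output is not truncated, which the documents do not show.

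**What to change.** In SAP 11.1.1, for Tables and Figures 14.2.2.5 and 14.2.2.6:

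1. Use Wilson intervals, or Clopper-Pearson if at least 95% coverage is wanted at every rate. Amend the method sentence, the table and figure descriptions, and the interval option in the sample code to match.
2. State which denominator, N or n*, each interval uses, and give the interval for whichever proportion is displayed.

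No new data are needed: the change is one method sentence, two labels, one SAS option and one sentence on the denominator. On timing, the existing addendum already notes that "These amendments were made post database lock but since the study was open label there was no unblinding step", so a further addendum is required. Showing the new intervals as supplementary, beside the prespecified Wald ones, avoids any appearance of a data-driven replacement.

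The cost in precision is small. At n = 20 Clopper-Pearson is wider than Wald at every count. Wilson is wider only at 0–2 and 18–20 of 20, and slightly narrower at 3–17.

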11.2 Additional Efficacy Endpoint(s)

The change from baseline in PACT scores (Forward Focus subscale, Trauma Focus subscale, and overall flexibility score) will be summarised, graphically displayed, and listed similarly to the secondary endpoints (*Table 14.2.3.1*, *Figure 14.2.3.1* and, *Listing 16.2.6.5*).

The 5D-ASC dimensions and EBI total score will be summarised (*Table 14.2.3.2* and *Table 14.2.3.3*, respectively) and listed (*Listing 16.2.6.7* and *Listing 16.2.6.8*, respectively).

The RAS total score will be listed (*Listing 16.2.6.6*).

12 CHANGES FROM THE PROTOCOL-PLANNED ANALYSES

Below is a list of changes from the protocol-planned analyses:

- Section 6 (Analysis Sets): The definition of FAS was updated to include those participants who do not have a post-baseline assessment
- Section 8.3.1 (Adverse Events): The AESI terms and MedDRA terms in AESI Table 5 have been updated from those included in the protocol to account for additional PTs of interest and updated MedDRA dictionary versions

13 DATA NOT PRESENTED

Data from the semi-structured qualitative interview, Cue app, fMRI, and blood biomarker components of the study will not be analysed for the CSR (clinical study report) so are not included in the scope of this SAP.

15 PROGRAMMING AND DATA PRESENTATION CONVENTIONS

15.1 Treatment Labelling

Table 14: Treatment Group Labels

COMP360 25 mg

15.2 Visit Labelling

Table 15: Analysis Visits and Output Labels

Analysis Visit	Output Label
Screening – Visit 1	Screening
Screening Period – Visit 1a/1b/1c/...	Screening a/ Screening b/Screening c/...
Baseline (Day -1) – Visit 2	Baseline or Day -1
Administration Session (Day 1) – Visit 3	Day 1
Day 2 – Visit 4	Day 2
Week 1 – Visit 5	Week 1
Week 2 – Visit 6	Week 2
Week 4 – Visit 7	Week 4
Week 6 – Visit 8	Week 6
Week 9 – Visit 9	Week 9
Week 12 (ET) – Visit 10	Week 12

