7 GENERAL CONSIDERATIONS

All TFLs will be created using SAS® version 9.4 or later.

Listings will be sorted in the following order: participant, visit, and parameter unless otherwise stated. All data will be listed.

Unless otherwise specified, “baseline” is defined as the last observed value of the parameter of interest prior to dosing. This includes values collected at both scheduled and unscheduled visits. For numerical variables, change from baseline will be calculated as the difference between the value of interest and the corresponding baseline value.

Continuous data will be summarised descriptively using n (number of observations), mean, standard deviation (SD), median, minimum, and maximum.

Categorical data will be summarised using frequency counts and percentages. The denominator for a percentage will be the total number of participants in the relevant treatment group or analysis set (N), unless otherwise specified (on some occasions, percentages may be calculated using the total number of participants with available data at a particular visit or time point as the denominator [n]).

Unscheduled visits and retests (same visit number assigned) will not be displayed in by-visit summary tables but will be included in the data listings.

All individual participant data will be listed. Listings will include scheduled, unscheduled, retest and early discontinuation data.

All medical histories, adverse events (AEs), and prior and concomitant non-drug therapy will be coded from the actual verbatim term using the Medical Dictionary for Regulatory Activities (MedDRA) version 26.1 or later.

All prior and concomitant medications will be coded using the World Health Organization (WHO) Drug Global Dictionary (Sep-2023 version or later).

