8.4 Efficacy Assessments

Unless otherwise stated, if any of items contributing to an instrument total score are missing then the total score will not be calculated.

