A total symptom severity score (range 0-80) can be obtained by summing the scores for each of the 20 items. The symptom cluster severity score can be obtained by summing the scores for the items within a cluster, as defined in Table 11.

Table 11: PCL-5 Item Mapping to Cluster

Criterion	Symptom Number
B	1, 2, 3, 4, 5
C	6, 7
D	8, 9, 10, 11, 12, 13, 14
E	15, 16, 17, 18, 19, 20

The PCL-5 ‘Screening’ version will be used at Screening (Visit 1). The ‘past day’ version will be used at Day 2 (Visit 2) and the ‘past week’ version of the assessment will be used at Baseline and at Weeks 1, 2, 4, 6, 9, and 12 (Visits 3, 5, 6, 7, 8, 9, and 10, respectively).

8.4.3 *Sheehan Disability Scale (SDS)*

The SDS is a brief, five-item self-report inventory assesses functional impairment in work/school (score ranges from 0 to 10), social life (score ranges from 0 to 10), and family

life (score ranges from 0 to 10).¹¹ The sum of the above three domain scores lead to a SDS total score ranging from 0 to 30 with 0 representing no impairment and 30 representing severe impairment. The past week version of the SDS will be performed.

For the main derivation, if the participant selects ‘I have not worked/studied at all during the past week for reasons unrelated to the disorder’, and has not answered the work/school item, the total score will be prorated by multiplying the scores of questions 2 (social life) and 3 (family life) by 1.5.

In addition to the main derivation, a sensitivity derivation will be calculated as follow: if a participant ticks the ‘I have not worked/studied at all during the past week for reasons unrelated to the disorder’ box and has not answered the work/school item, then no SDS total score will be derived.

The SDS data will be obtained at Baseline, Week 4, and Week 12 (Visits 2, 7, and 10, respectively).

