9 STUDY PARTICIPANTS

9.1 Disposition of Participants

The summaries will be presented overall.

The number of participants screened, screen failures, and the number and percentage of participants in each analysis set will be summarised by country and overall, for the Screening Analysis Set (*Table 14.1.1.1*). The number and percentage of participants who completed the study and number and percentage of participants who discontinued from the study, with reasons for discontinuation, will be summarised using the Safety Analysis Set (*Table 14.1.1.2*). The reasons for screen failures will also be tabulated (*Table 14.1.1.3*).

Participant disposition will be listed by study discontinuations (*Listing 16.2.1.1*) and completers (*Listing 16.2.1.2*) using the Safety Analysis Set. Participation in each defined analysis set will be listed using the Screening Analysis Set (*Listing 16.2.3*). Inclusion criteria not met/exclusion criteria met at Screening and at Baseline will be listed using the Screening Analysis Set (*Listing 16.2.4.4* and *Listing 16.2.4.5*).

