10.2 Laboratory Tests

Descriptive statistics of the observed values and change from baseline (continuous data) will be presented for each haematology (*Table 14.3.4.1*) and chemistry (*Table 14.3.4.2*) parameter by visit.

Shift tables will display numbers of participants with normal range shifts at baseline versus post-treatment at Day 2, Week 4, and Week 12 (*Table 14.3.4.3* and *Table 14.3.4.4* for haematology and chemistry, respectively).

Listings for haematology, chemistry, and urinalysis data (*Listing 16.2.8.1*, *Listing 16.2.8.2*, and *Listing 16.2.8.3*) will also flag values that are outside normal reference ranges or markedly abnormal findings. Clinically significant laboratory data will also be listed separately (*Listing 16.2.8.4*).

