16 TABLES, FIGURES AND LISTINGS

The following tables include details of the tables, figures and listings to be created.

The following validation methods may be used:

- Independent programming of numbers and manual review of format (Iprog)
- Independent programming by statistician of numbers and manual review of format (Stat Iprog)
- Manual review (MR)
- Code review (CR)

Table 18: List of Tables, Figures and Listings

Table Number	Table Title	Validation Method	Shell Number (if Repeat)
14.1	Demographic Data		
14.1.1	Disposition		
14.1.1.1	Participant Disposition by Country – Screening Analysis Set	IProg	
14.1.1.2	Participant Disposition, Completions, and Early Terminations with Reasons – Safety Analysis Set	IProg	
14.1.1.3	Screen Failures with Reasons – Screening Analysis Set	IProg	
14.1.1.4	Important Protocol Deviations – Safety Analysis Set	IProg	
14.1.2	Demographics		
14.1.2	Demographics – Safety Analysis Set	IProg	
14.1.3	Baseline Characteristics		
14.1.3.1	Medical History – Safety Analysis Set	IProg	
14.1.3.2	Prior Medications – Safety Analysis Set	IProg	
14.1.3.3	Concomitant Medications – Safety Analysis Set	IProg	14.1.3.2
14.1.3.4	Prior Non-Drug Therapies – Safety Analysis Set	IProg	14.1.3.1
14.1.3.5	Concomitant Non-Drug Therapies – Safety Analysis Set	IProg	14.1.3.1
14.1.3.6	Prior Non-Drug Therapies for PTSD – Safety Analysis Set	IProg	14.1.3.1
14.1.3.7	Concomitant Non-Drug Therapies for PTSD – Safety Analysis Set	IProg	14.1.3.1
14.1.3.8	Other Baseline Characteristics – Safety Analysis Set	IProg	
14.1.3.9	Mini International Neuropsychiatric Interview (MINI, Version 7.0.2) – Safety Analysis Set	IProg	
14.1.3.10	Life Event Checklist for DSM-5 (LEC-5) – Safety Analysis Set	IProg	
14.2	Efficacy Data		
14.2.2	Secondary Efficacy Endpoints		
14.2.2.1	Secondary Endpoint – Summary of Clinician-Administered PTSD Scale for DSM-5 (CAPS-5) and Change from Baseline – Full Analysis Set	IProg	

Table Number	Table Title	Validation Method	Shell Number (if Repeat)
14.2.2.2	Secondary Endpoint – Summary of PTSD Checklist for DSM-5 (PCL-5) and Change from Baseline – Full Analysis Set	IProg	14.2.2.1
14.2.2.3	Secondary Endpoint – Summary of Sheehan Disability Scale (SDS) Total Score and Change from Baseline – Full Analysis Set	IProg	14.2.2.1
14.2.2.4	Secondary Endpoint – Summary of EQ-5D-5L Index Score and Change from Baseline – Full Analysis Set	IProg	14.2.2.1

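### The SAP gives scheduled Week 12 and early-termination visits the one label Week 12, with no window or rule to separate them, so earlier results are summarised as Week 12

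*SAP*

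**What the plan says.** SAP Table 15 (section 15.2) lists the final analysis visit as "Week 12 (ET) – Visit 10" and gives it the output label Week 12. The last column of the SAP schedule (section 4.3, Table 2) likewise puts ET in parentheses after Week 12. No other label exists for an ET visit.

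Two sentences in SAP section 7 bear on what enters the tables. The exclusion is "Unscheduled visits and retests (same visit number assigned) will not be displayed in by-visit summary tables". Early-discontinuation data are named only for listings: "Listings will include scheduled, unscheduled, retest and early discontinuation data".

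Section 15 otherwise holds timepoint labels, baseline definitions, study-day formulas and decimal conventions. It has no analysis window and no ET rule. Section 12 (changes from the protocol) and the addendum add none.

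The supplied protocol (7.2.10 and 7.3) has participants who stop early complete the Visit 10 assessments, with no minimum time since dosing. It may not be the V5.0 protocol that SAP section 1 cites: it lacks BPRS+, 5D-ASC, EBI and mDESS. The SAP's own two tables carry the mapping without it.

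**The concern.** The by-visit summaries are the whole efficacy result of this study: there is no model and no test. What they say depends on the visit label. An ET score filed under Week 12 acts like an earlier observation carried forward, which the SAP nowhere declares.

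The label reaches every summary with a Visit 10 column: CAPS-5, PCL-5, SDS, EQ-5D-5L, PACT, response and remission, C-SSRS and BPRS+. It also reaches the laboratory tables, where "Shift tables will display numbers of participants with normal range shifts at baseline versus post-treatment at Day 2, Week 4, and Week 12", and the addendum's Week 12 CAPS-5 plots. AE, ECG and vital-sign tables are not affected.

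Section 11.1.1 reports response and remission on FAS N and on n*, those with data at the visit. Pooling blurs both. On N, an ET responder is added to a fixed denominator, so the rate can only rise. On n*, people with no Week 12 assessment are counted as having one, and the rate can move either way. CAPS-5 also uses the last-month version, so an ET score from the first month after dosing partly describes pre-dose symptoms.

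**Working it through.** The plan states no figure that depends on this point, so there is none to reproduce. The check is of the text first, then of size under stated assumptions.

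**Does any rule remove or re-slot ET data?**

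- The section 7 exclusion names unscheduled visits and retests, not ET.
- The section 7 listing sentence also names scheduled data, so being listed does not imply being left out of tables.
- Treating ET as unscheduled would contradict Table 15, which names ET within Visit 10.
- The ±7 days in Table 2 is a visit allowance; nothing makes it an analysis window.
- Section 8.4 is a partial filter only: "if any of items contributing to an instrument total score are missing then the total score will not be calculated". An incomplete ET instrument drops out; a complete one enters.

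**Study days.** Section 15.5 makes dosing Day 1, so week w falls on Day 7w + 1. With the Table 2 allowances: Week 1, Days 7–9; Week 2, 14–16; Week 4, 28–30; Week 6, 40–46; Week 9, 61–67; Week 12, 78–92. A post-dose ET visit before the Week 12 window can fall on any of Days 2–77, which is 76 days.

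**Response rate.** Assumptions: 20 dosed; k ETs, each attending before Day 78 with a complete score; all 20 − k completers scored at Week 12, 10 of them responders; e of the k ETs respond.

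- As labelled: (10 + e)/20 on both N and n*.
- ET separated: 10/20 on N and 10/(20 − k) on n*.
- Shift on N = e/20, never negative.
- Shift on n* = (10 + e)/20 − 10/(20 − k).

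| k | As labelled | Separated, N | Separated, n* | Shift on N (points) | Shift on n* (points) |
|---|---|---|---|---|---|
| 1 | 50.0 to 55.0% | 50.0% | 10/19 = 52.6% | 0 to +5.0 | −2.6 to +2.4 |
| 2 | 50.0 to 60.0% | 50.0% | 10/18 = 55.6% | 0 to +10.0 | −5.6 to +4.4 |
| 3 | 50.0 to 65.0% | 50.0% | 10/17 = 58.8% | 0 to +15.0 | −8.8 to +6.2 |

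The lower end has no ET responding (e = 0), the upper end all of them (e = k).

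**Against the planned interval.** Wald half-width = 1.96 × √(p(1 − p)/n).

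- 13/20 = 65.0%: ±20.9, so 44.1 to 85.9.
- 10/20 = 50.0%: ±21.9, so 28.1 to 71.9.
- 10/17 = 58.8%: ±23.4, so 35.4 to 82.2.

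Every shift in the table is smaller than these half-widths.

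**Mean change.** If ETs differ from completers by d points, the pooled mean moves by (k/20) × d. For k = 1, 2, 3 that is 0.5, 1.0, 1.5 points when d = 10, and 1, 2, 3 points when d = 20.

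**If ET is assigned by window, how often is it in no earlier window?** An instrument can be assigned to a visit only where it is scheduled with the same recall period. For PCL-5 the past-week "version of the assessment will be used at Baseline and at Weeks 1, 2, 4, 6, 9, and 12" (section 8.4.2), while Day 2 takes the past-day version, so Day 2 does not count.

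| Instrument | In-window days of 76 | Outside |
|---|---|---|
| CAPS-5, SDS, EQ-5D-5L, PACT | 3 (Week 4) | 73 (96%) |
| Laboratory | 4 (Day 2, Week 4) | 72 (95%) |
| PCL-5 | 3 + 3 + 3 + 7 + 7 = 23 | 53 (70%) |
| BPRS+, C-SSRS | 24 (as PCL-5, plus Day 2) | 52 (68%) |

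The outside counts are minima: an in-window ET record also stays out when a scheduled record already exists at that visit.

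**The case against.** The SAP never states that ET results are tabulated as Week 12, and the table shells, which are not in the documents, might flag them. The first part stands: the pooling is an inference. Nothing in the available text contradicts it, and the listings-only reading of section 7 fails for the reason given above.

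The size may well be small. After one supervised dose there is no further study drug to stop. The supplied protocol follows participants who restart medication to Week 12, and those lost to follow-up attend no ET visit. Lack of efficacy and adverse events are listed reasons for termination, so three attended ETs that all respond is an extreme case. This stands; the 15-point figure is an upper end under assumption, not a forecast.

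Separating ET is not neutral either. It makes the Week 12 mean describe attenders only, counts an observed ET responder as a non-responder on N, and with three non-responding ETs raises n* from 50.0% to 58.8%. This also stands, and is why the ET values must be shown beside Week 12 rather than dropped.

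Finally, discontinuations are already tabulated ("Participant Disposition, Completions, and Early Terminations with Reasons", Table 14.1.1.2), all data are listed, and the addendum adds individual CAPS-5 plots. A reader can trace an ET value, but the Week 12 tables themselves do not show which values are ET values. A footnote alone would disclose the problem and leave the headline rates mislabelled.

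**Conclusion.** The concern holds. Table 15 maps ET and scheduled Week 12 to one label and nothing in the SAP or addendum undoes it, so an attended post-dose ET assessment with a complete score or result is reported as Week 12.

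The documents do not give the number of ETs, and with none attended the effect is nil. With one to three among 20, under the assumptions above, the N-based response rate is overstated by 0 to 15.0 points, in that direction only. The n*-based rate shifts by −8.8 to +6.2 points. These shifts are smaller than the Wald half-widths of about 21 to 23 points. No hypothesis is tested and section 11 calls the intervals exploratory. The harm is a wrong time point on descriptive results, worth correcting but not a failed analysis.

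**What to change.** In section 15.2, give ET its own output label and add these rules:

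- Scheduled Visit 10 records of completers stay Week 12, whatever their exact day.
- An ET record is Week 12 only if it falls on Days 78–92.
- It goes to another scheduled visit only if that instrument is due there with the same recall version, the record lies in that visit's window, and no scheduled record exists.
- Otherwise it appears in a separate ET row. At Week 12 the participant is then missing for n* and a non-responder and non-remitter for N.
- Week 12 tables carry a footnote with the number of ETs and their study days.

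The cost is a mapping change and a rerun of the affected tables, with no new data. The existing addendum already postdates database lock in an open-label study, so this change has to be declared post hoc, with the original mapping kept as a sensitivity summary. Week 12 n falls, and the Week 12 mean must be read with the ET row. Most ET records will land in that row (at least 96% of possible days for CAPS-5). With one to three ETs it is sparse and mixes study days, hence the footnote. If no ET visit was attended, one sentence saying so settles the point.
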